1.6.1.2 Trametinib (Mekinist®)

The safety profile of trametinib has been well established and detailed in the product's package insert and IB. The most common adverse reactions (occurring in greater than 20% of patients) include rash, diarrhea, and lymphedema (package insert). Additional common side effects (occurring in greater than 10% of patients) dermatitis acneiform, dry skin, pruritis, paronychia, stomatitis, abdominal pain, hypertension, and hemorrhage (package insert). Additional side effects (occurring in less than 10% of patients) include blurred vision, dry eye, dizziness, dysgeusia, folliculitis, pustular rash, cellulitis, bradycardia, cardiomyopathy, xerostomia, and rhabdomyolysis (package insert). Rare adverse events (occurring in less than 5% of patients) include retinal pigment epithelial detachment (RPED), retinal vein occlusion (EVO), and interstitial lung disease (package insert). Laboratory abnormalities (occurring in greater than 5% of patients) include increased AST, increased ALT, hypoalbuminemia, anemia, and increased alkaline phosphatase (package insert).

Trametinib is an inducer of CYP3A4 *in vitro*. However, trametinib's efficacious dose of 2 mg once daily results in a low systemic maximal concentration (22.2 ng/mL or 0.036 μM), relative to its *in vitro* inhibition potency of CYP enzymes and transporters, rendering the risk of an inhibitory effect of trametinib on the PK of co-administered CYP or transporter substrates low. Trametinib is eliminated primarily via deacetylation and possibly other hydrolases. There is little evidence from clinical studies for drug interactions mediated by carboxylesterases. Trametinib is also a substrate of P-gp and BSEP. However, due to its high passive permeability, these active transport processes are likely of limited relevance. Therefore, a clinically relevant effect of a co-administered P-gp or BSEP inhibitor on the PK of trametinib is unlikely.

1.6.1.2.1 Management of Toxicity Related to Trametinib

CONFIDENTIAL

This material is the property of the NYU School of Medicine and Langone Medical Center. Do not disclose or use except as authorized in writing by the study sponsor

Table 1. Recommended Dose Modifications for Trametinib

Target Organ	Adverse Reaction^a	Dose Modification
Cutaneous	Grade 2 rash (tolerable)	Continue treatment and monitor
	Intolerable Grade 2 rash or Grade 3 or 4 rash	Withhold Trametinib for up to 3 weeks If improved within 3 weeks, resume Trametinib at a lower dose (reduced by 0.5 mg) or discontinue Trametinib in patients taking Trametinib 1 mg daily
	Intolerable Grade 2 or Grade 3 or 4 rash that does not improve within 3 weeks despite interruption of Trametinib dosing	Permanently discontinue Trametinib
Cardiac	Asymptomatic, absolute decrease in LVEF of 10% or greater from baseline and is below institutional lower limits of normal (LLN) from pretreatment value	Withhold Trametinib for up to 4 weeks. If improved within 4 weeks, resume Trametinib at a lower dose (reduced by 0.5 mg) or discontinue Trametinib in patients taking Trametinib 1 mg daily
	
 - Symptomatic congestive heart failure - Absolute decrease in LVEF of greater than 20% from baseline that is below LLN - Absolute decrease in LVEF of 10% or greater from baseline and is below LLN that does not improve to normal LVEF value within 4 weeks following interruption of Trametinib 	Permanently discontinue Trametinib
Ocular	Grade 2-3 retinal pigment epithelial detachments (RPED)	Withhold Trametinib for up to 3 weeks. If improved to ≤ Grade 1 within 3 weeks, resume Trametinib at a lower dose (reduced by 0.5 mg) or discontinue Trametinib in patients taking Trametinib 1 mg daily. If it does not improve to ≤ Grade 1 within 3 weeks, discontinue Trametinib.

CONFIDENTIAL

Ocular	Retinal Vein Occlusion	Permanently discontinue Trametinib
Pulmonary	Interstitial lung disease/pneumonitis	Permanently discontinue Trametinib
Other	Intolerable Grade 2 adverse reaction Grade 3 adverse reaction	Withhold Trametinib for up to 3 weeks. If Grade 3 adverse reaction improves to \leq Grade 1 following interruption of Trametinib within 3 weeks then reduce dose of Trametinib by 0.5mg or discontinue Trametinib in patients taking Trametinib 1 mg daily.
	Grade 4 adverse reaction or Grade 3 adverse reaction that does not improve to Grade 0-1 within 3 weeks	Permanently discontinue Trametinib

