1.6.2 Overlapping Toxicities

Unless a side effect is specific to only trametinib (cardiac (red LVEF), ocular (RPED, RVO), and/or pneumonitis), both drugs should be held together. With the exception of the trametinib specific side effects, all other side effects can be considered from either medication.

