1.6.3 Dose-Limiting Toxicities

For this study, DLT is defined as all toxicities regardless of attribution to study drug, with the exception of toxicities clearly due to disease progression or identified extraneous cause.

The following AEs will be considered to be DLTs:

- Any toxicity that requires permanent discontinuation of either drug. Note: this would include retinal vein occlusion, interstitial lung disease, and any toxicity identified in the dose modification guidelines for CDX-3379.
- Any toxicity regardless of grade that requires an interruption of more than 4 weeks.
- Any fatal adverse event.

Hematologic Toxicity:

-Grade 4 neutropenia (absolute neutrophil count (ANC) < 500/ul) lasting > 7 days.

CONFIDENTIAL

- Febrile neutropenia (ANC<1,000/ul).
- Grade 4 thrombocytopenia (platelet count < 25,000/ul).
- Grade 3 thrombocytopenia (platelet count 25,000/ul to 50,000/ul) with clinically important bleeding.

Nonhematologic Toxicity:

All other Grade 3 or higher nonhematologic toxicities with the following exceptions:

- Alopecia
- Grade 3 nausea, vomiting, and/or diarrhea that lasts <72 hours with adequate antiemetic and supportive care.
- Grade 3 electrolyte abnormalities that are asymptomatic and last ≤ 24 hours with medical intervention.

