No of pts	Cohort Level	CDX-3379	Trametinib
6	1	15mg/kg IV Q 3wks	2mg daily
6	-1A	15mg/kg IV Q 3wks	1.5mg daily
6	-1B	10 mg/kg IV Q 3wks	1.5mg daily
6	-2A	10mg/kg IV Q 3wks	1.0 mg daily
6	-2B	5 mg/kg IV Q 3wks	1.0mg daily

Safety has been established for the combination of CDX-3379 (ERBB3 antibody) and chemotherapeutic agents and targeted therapy at the standard doses with maximum dose of 20mg/kg. In addition, the recommended treatment dose of trametinib is 2mg. However, no data is available for the combination of CDX-3379 (ERBB3 antibody) and trametinib. In Phase Ib, all patients will start treatment at the cohort 1 doses. Six patients will be enrolled at this dose level and monitored for DLTs for 6 weeks (which is two treatment cycles (42 days)).

[figure not shown]
In these six participants, if none or one subject experiences a DLT, then dose cohort 1 will be considered the RP2D, and phase II of the clinical trial will proceed. After the first 20 patients are enrolled in the initial cohort, enrollment will be placed on hold to monitor for toxicity. At this point, a stopping rule for the cohort expansion portion of the trial for excessive toxicity such that if $\geq 30\%$ of patients enrolled across groups discontinue treatment due to toxicity, enrollment will pause and an assessment of the toxicity of the treatment regimen(s) will be performed. This assessment, along with justification for resumption of enrollment, should be submitted to FDA. This stopping rule for the cohort expansion portion of the trial for excessive toxicity applies regardless of which dose is selected as the RP2D. Toxicities will be reviewed by study sponsor (NYU Langone Health) and DSMC. If $\leq 33\%$ of patients experience DLT based on review, then the study will continue enrollment. If $> 33\%$ of patients experience a DLT, then the study sponsor (NYU Langone Health), DSMC will convene to determine the best course of action (i.e. enrollment at decreased dosing cohort, etc).

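### Table 1's two cardiac rows give opposite orders, restart or stop trametinib for good, when LVEF has partly recovered but is still below normal at four weeks

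*Combined protocol and SAP*

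**What the plan says.** The rules are in the protocol, section 1.6.1.2.1, Table 1, Cardiac rows.

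- **First row, trigger:** an asymptomatic patient with an "absolute decrease in LVEF of 10% or greater from baseline and is below institutional lower limits of normal (LLN) from pretreatment value".
- **First row, action:** hold trametinib for up to four weeks, then "If improved within 4 weeks, resume Trametinib at a lower dose (reduced by 0.5 mg"; patients already on 1 mg are discontinued. The row gives no target value for the improvement.
- **Second row:** permanent discontinuation on any of three conditions. The first is symptomatic heart failure. The second is "Absolute decrease in LVEF of greater than 20% from baseline that is below LLN". The third takes the first row's fall (10% or greater) and applies when it is "below LLN that does not improve to normal LVEF value within 4 weeks following interruption of Trametinib".

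Three other places bear on the consequences:

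- Section 1.6.2 exempts LVEF reduction from the joint hold of both drugs: "Unless a side effect is specific to only trametinib (cardiac (red LVEF), ocular (RPED, RVO), and/or pneumonitis), both drugs should be held together".
- Section 1.6.3 counts as a DLT "Any toxicity that requires permanent discontinuation of either drug" and also "Any toxicity regardless of grade that requires an interruption of more than 4 weeks".
- Section 3.1 has the Phase Ib patients "monitored for DLTs for 6 weeks (which is two treatment cycles (42 days" in total), while section 6.7, footnote 15, schedules echocardiogram or MUGA only every 12 weeks, or at the physician's discretion.

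**The concern.** The two rows start from the same event but use different recovery standards. The first restarts on any improvement; the second stops unless LVEF is normal again. A patient who has improved but is still below LLN at four weeks satisfies both, and an investigator could follow either row and be within the protocol.

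The first consequence is for the patient. The first row, taken as written, allows trametinib to be restarted while LVEF is subnormal. Section 1.4.2 lists decreased ejection fraction among the drug's treatment-related events (7%), and section 4.1 requires LVEF of at least 50% at entry. Because section 1.6.2 removes reduced LVEF from the joint-hold rule, Table 1 is the visible guidance on restarting.

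The second consequence is classification. For an event below Grade 3, a hold of up to four weeks followed by a restart is not a DLT under the interruption clause, but a permanent stop is a DLT under the discontinuation clause. The choice of row can therefore decide DLT status. A second site is planned (section 4.4), so the same case could be handled and counted differently at the two sites.

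**Working it through.** There is no plan figure to reproduce. The check sets the two rows side by side, then works examples.

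**Inputs from Table 1.** Hold trigger: fall from baseline of at least 10 points and LVEF below LLN, without symptoms. Unconditional stop: fall of more than 20 points and below LLN. **Assumption:** the LLN, which the protocol leaves to the institution; 50% is used, with a range of 45% to 55%.

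**Step 1. Where the rows collide** (asymptomatic fall, below LLN, dose above 1 mg):

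| Fall | LVEF at 4 weeks | First row | Second row |
|---|---|---|---|
| 10–20 points | at or above LLN | restart lower | does not apply |
| 10–20 points | improved, still below LLN | **restart lower** | **stop permanently** |
| 10–20 points | not improved | no restart | stop permanently |
| more than 20 points | any | – | stop permanently, by its second condition |

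Only the second line is in conflict. The last line is treated as settled because the second row requires a stop whatever the recovery.

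**Step 2. Worked case.** LLN 50%, baseline 62%, held at 46%, week-four value 49%.

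- Fall at hold: 62 − 46 = 16 points, between 10 and 20, and 46 < 50, so trametinib is held.
- Week four: 49 > 46, so LVEF has improved and the first row restarts.
- Week four: 49 < 50, so LVEF is not normal and the second row stops.

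**Step 3. The first row against itself.** At week four the patient is 62 − 49 = 13 points below baseline and below LLN, so the first row's own hold trigger is still met when it restarts the drug. In general, let B be the baseline and W the week-four value. If B ≥ LLN + 10 and W < LLN, then B − W > (LLN + 10) − LLN = 10. For an LLN of 45%, 50% or 55%, this covers every subnormal week-four value once baseline is at least 55%, 60% or 65%.

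**Step 4. Lower baseline.** LLN 50%, baseline 55%, held at 44% (55 − 44 = 11 points), week four 48% (55 − 48 = 7 points). The hold trigger is no longer met, but the rows still disagree: 48 > 44 restarts, 48 < 50 stops.

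**Step 5. Dose levels.** At 1 mg the first row also discontinues, so there is no conflict. In the section 3.1 cohort table, levels 1 (2 mg), −1A and −1B (1.5 mg each) start above 1 mg; −2A and −2B start at 1 mg. The conflict exists at the starting dose of 3 of 5 levels.

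**Step 6. DLT timing.** For a full four-week hold to end inside the 42-day window, the fall must be found by day 42 − 28 = 14. The first scheduled on-treatment echo is at 12 × 7 = day 84, so an unscheduled echo would be needed.

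**The case against.** The best reply is that the rows are a sequence. The third condition of the second row repeats the first row's fall and refers to the interruption, so it is the follow-on for a patient already held. On that reading the first row is merely unspecific, and the reader takes the recovery standard from the next row, which is the more specific of the two. That the first row alone would restart the drug on a value meeting its own hold trigger supports this reading.

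This is probably the intent, but the text does not say it, and the rest of Table 1 does not help. For rash, a bare improvement is paired with its exact complement. For retinal pigment epithelial detachment, Grade 1 or less governs both restarting and stopping. For other Grade 3 reactions, Grade 1 or less is matched with Grade 0–1. Elsewhere, then, restart and stop endpoints match; the cardiac pair is the exception.

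Several points on the other side do stand:

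- The table's column heading carries a footnote whose text is not visible, and the package insert and Investigator's Brochure are attachments that were not available. Any of these might define cardiac recovery.
- The effect on the Phase Ib rule of two DLTs in six patients is small, given Step 6. The day-14 limit is itself an inference, because the protocol does not say whether a later discontinuation counts for a toxicity that began inside the window.
- The 7% is any ejection-fraction decrease in a dose-escalation population and does not size this subset. The 3 of 5 counts dose levels, not patients.
- No endpoint, sample size or efficacy analysis changes.

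**Conclusion.** The concern holds: the restart rule is wrong as written. For an asymptomatic fall of 10 to 20 points to below LLN, with partial recovery still below LLN at four weeks, in a patient on more than 1 mg, Table 1 orders both a restart and a permanent stop. Followed literally, the first row restarts trametinib at a subnormal LVEF. When baseline is at least 10 points above LLN, it does so on a value that still meets its own hold trigger.

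The conflict does not depend on the LLN chosen; the numerical cases do, and the LLN values are assumptions. The conclusion also assumes that the unseen footnote does not rank the rows or define improvement. The documents give no rate for this situation, so no frequency is estimated. It should seldom affect the Phase Ib dose decision. The stronger reason to correct it is individual dosing, which continues throughout treatment, when the 12-weekly echoes can detect such falls. It should be corrected, though it does not threaten the trial's main conclusions.

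**What to change.** In the first cardiac row, make the restart conditional on LVEF having improved to a normal value, at or above the institutional LLN, within four weeks. Leave the second row and section 1.6.3 unchanged. The restart and stop conditions then exclude each other, using the endpoint the second row already states. Optionally, cap the first row's trigger at a 20-point fall so that larger falls appear only in the second row.

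The cost is a few words in one table row. No patients are added, and no test is added, since both rows already need a repeat LVEF value by four weeks. The downside is that a few partly recovered patients will stop trametinib and, if within the DLT window, count as DLTs; the second row already requires that stop.

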1.6.2 Overlapping Toxicities

Unless a side effect is specific to only trametinib (cardiac (red LVEF), ocular (RPED, RVO), and/or pneumonitis), both drugs should be held together. With the exception of the trametinib specific side effects, all other side effects can be considered from either medication.

1.6.3 Dose-Limiting Toxicities

For this study, DLT is defined as all toxicities regardless of attribution to study drug, with the exception of toxicities clearly due to disease progression or identified extraneous cause.

The following AEs will be considered to be DLTs:

- Any toxicity that requires permanent discontinuation of either drug. Note: this would include retinal vein occlusion, interstitial lung disease, and any toxicity identified in the dose modification guidelines for CDX-3379.
- Any toxicity regardless of grade that requires an interruption of more than 4 weeks.
- Any fatal adverse event.

Hematologic Toxicity:

-Grade 4 neutropenia (absolute neutrophil count (ANC) < 500/ul) lasting > 7 days.

CONFIDENTIAL

- Febrile neutropenia (ANC<1,000/ul).
- Grade 4 thrombocytopenia (platelet count < 25,000/ul).
- Grade 3 thrombocytopenia (platelet count 25,000/ul to 50,000/ul) with clinically important bleeding.

Nonhematologic Toxicity:

All other Grade 3 or higher nonhematologic toxicities with the following exceptions:

- Alopecia
- Grade 3 nausea, vomiting, and/or diarrhea that lasts <72 hours with adequate antiemetic and supportive care.
- Grade 3 electrolyte abnormalities that are asymptomatic and last ≤ 24 hours with medical intervention.

1.6.4 Other Risks of Study Participation

Risks of study participation may be that the drugs under study will not be effective for some participants. In this case, the study drugs will be discontinued and participants will continue regular care by their provider to determine the next appropriate step in therapy. The study may also require additional outpatient visits, blood tests, and tissue biopsies that may otherwise not be required off study. The risks associated with blood draw include weakness, redness, pain, bruising, bleeding, or infection at the needle site. The effects of FNA and core biopsies are generally mild; slight discomfort and light bleeding are to be expected. Participants have the option of discontinuing study treatment at any time. Trial investigators will determine the appropriate drug dose and will administer this in the phase 2 portion of the trial. There has been clinical experience previously with all of the study drugs and investigators will continually monitor for adverse events.

1.6.5 Potential Benefit

Participants participating in the research study will have access to combination therapy with trametinib and CDX-3379, an ERBB3 inhibitor. The information obtained from this research may help others with this disease in the future. Subjects' health may improve while on the trial, but it may not. It is hoped that results from this trial may help others with this disease.

2 Study Objectives

Primary Objectives:

Phase 1b: To determine the MTD/RP2D and assess the toxicity and tolerability of the combination of CDX-3379 (ERBB3 antibody) and trametinib (MEK inhibitor) in *NRAS* and *BRAF/NRAS* WT melanoma patients

Phase 2: To estimate the response rate and duration of response of the combination CDX-3379 and trametinib in *NRAS* mutant and *BRAF/NRAS* WT melanoma patients

Secondary/Exploratory Objectives:

Phase 2: To compare the efficacy of the combination of CDX-3379 (ERBB3 antibody) and trametinib is more effective than a MEK inhibitor alone in *NRAS* positive and *BRAF/NRAS* WT melanoma patients alone using locally assessed progression free survival (PFS) and overall survival (OS)

CONFIDENTIAL

Exploratory Objectives:

To evaluate ERBB3 signaling pathway and MAPK signaling pathway components, in addition to pathway ligands, including NRG1/HRG1 (neuregulin 1/heregulin 1, ERBB3 ligand) expression and correlate this with treatment response.

- archival tissue and pre-treatment, on treatment, and progression tumor samples will also be obtained for all patients in Phase Ib and the first 5 patients with *NRAS* mutant melanoma and the first 5 patients with WT melanoma in Phase II.

[figure not shown]
3 Study Design

3.1 General Design

This study is an open-label, non-randomized phase Ib/II study in patients with unresectable stage III or stage IV *NRAS* mutant or *BRAF/NRAS* WT melanoma.

Following signing informed consent and evaluation of initial eligibility criteria, all participants will provide an archived tissue sample (which meets the requirements for collection and processing as outlined in the study lab manual). In addition, all patients enrolled on Phase Ib and the first five *NRAS* mutant melanoma participants and first five WT melanoma participants on Phase II will undergo a mandatory core biopsy for pretreatment tumor tissue. For these procedures, investigators are asked to choose an easily accessible tumor lesion to minimize any possible risk associated with the collection of the tissue. As a general guideline, if the selected procedural location of the core needle biopsy or FNA has an established serious complication rate of >2% at the institution completing the procedure, this is considered a high risk procedure and should be avoided.

The purpose of this phase Ib study is to determine the MTD/RP2D and assess the toxicity and tolerability of combination of CDX-3379 (ERBB3 inhibitor) and trametinib (MEK inhibitor) in *NRAS* mutant and WT advanced stage melanoma. The purpose of phase II study is to estimate the response rate and duration of response of the combination in each cohort of participants that are *NRAS* mutant and WT advanced stage melanoma

Abbreviations: C = cycle; D = day; PD = progressive disease.

Figure 1: Phase Ib study design

Phase 1b: 6-18 evaluable subjects will be treated to identify the MTD/RP2D prior to advancing to phase II.

CONFIDENTIAL

This material is the property of the NYU School of Medicine and Langone Medical Center. Do not disclose or use except as authorized in writing by the study sponsor

Definition of MTD/RP2D -

Once the subject has completed the screening procedures and is deemed eligible for the study, the subjects will be assigned to the following therapy:

Trametinib: 2 mg PO daily
ERBB3 antibody (CDX-3379) 15mg/kg IV on day 1 of each 21-day cycle

MTD/RPRD will be determined by combining ERBB3 antibody (CDX-3379) 15mg/kg IV Q3W with 2mg trametinib. Dose de-escalation of ERBB3 antibody (CDX-3379) and/or trametinib, if needed, will be allowed if significant toxicity is experienced with the two drugs at their recommended doses (which were previously determined).

Cohort levels for MTD/RP2D:

No of pts	Cohort Level	CDX-3379	Trametinib
6	1	15mg/kg IV Q 3wks	2mg daily
6	-1A	15mg/kg IV Q 3wks	1.5mg daily
6	-1B	10 mg/kg IV Q 3wks	1.5mg daily
6	-2A	10mg/kg IV Q 3wks	1.0 mg daily
6	-2B	5 mg/kg IV Q 3wks	1.0mg daily

Safety has been established for the combination of CDX-3379 (ERBB3 antibody) and chemotherapeutic agents and targeted therapy at the standard doses with maximum dose of 20mg/kg. In addition, the recommended treatment dose of trametinib is 2mg. However, no data is available for the combination of CDX-3379 (ERBB3 antibody) and trametinib. In Phase Ib, all patients will start treatment at the cohort 1 doses. Six patients will be enrolled at this dose level and monitored for DLTs for 6 weeks (which is two treatment cycles (42 days)).

[figure not shown]
In these six participants, if none or one subject experiences a DLT, then dose cohort 1 will be considered the RP2D, and phase II of the clinical trial will proceed. After the first 20 patients are enrolled in the initial cohort, enrollment will be placed on hold to monitor for toxicity. At this point, a stopping rule for the cohort expansion portion of the trial for excessive toxicity such that if $\geq 30\%$ of patients enrolled across groups discontinue treatment due to toxicity, enrollment will pause and an assessment of the toxicity of the treatment regimen(s) will be performed. This assessment, along with justification for resumption of enrollment, should be submitted to FDA. This stopping rule for the cohort expansion portion of the trial for excessive toxicity applies regardless of which dose is selected as the RP2D. Toxicities will be reviewed by study sponsor (NYU Langone Health) and DSMC. If $\leq 33\%$ of patients experience DLT based on review, then the study will continue enrollment. If $> 33\%$ of patients experience a DLT, then the study sponsor (NYU Langone Health), DSMC will convene to determine the best course of action (i.e. enrollment at decreased dosing cohort, etc).

If two or more of the six subjects experience DLT, we will consider the initial dose cohort beyond the MTD and we will enroll six more patients in cohort 1A or 1B, based on the toxicity pattern observed that is felt to be attributed to a particular drug. Dose reduction to -1A or -2A is specifically for toxicity related to trametinib, LVEF reduction, RPED, pneumonitis and LFT abnormalities. -1A is the first reduction, followed by -2A as the second reduction. For all other observed toxicities the default dose-reduced cohort is -1B followed by -2B. In the new dose cohort, if none or one patient experiences a DLT, then the study will open to full enrollment on the Phase II portion of the trial. If two or more of these additional six patients experience DLT, we will then enroll six

CONFIDENTIAL

additional patients at additional dose de-escalation cohorts, to be determined by sponsor (NYULMC) and NYU DSMC), again based on toxicity pattern observed and drug attribution. If two or more patients experience DLT at this new dose cohort, then the trial will be terminated.

Phase 2: There are two Arms - Arm A (*NRAS* mutant melanoma patients) and Arm B (WT melanoma patients). This is the first part of a Simon Minimax design. Each arm will initially enroll 19 subjects. If there are three or fewer responses, then accrual to that cohort will be stopped. Otherwise, the study will be amended to enroll a total of 36 subjects to each approved arm/cohort.

Abbreviations: C = cycle; D = day; PD = progressive disease.

Figure 2: Phase II study design

Translational Research -

We will perform biopsies on all phase Ib patients (expected 6 patients, but could be up to 18) and five patients on each Arm of the study for Phase II. Biopsies will be obtained pre-treatment, on-treatment between day 14-16, and at the time of disease progression. Archival tissue will also be collected. We will investigate pathway inhibition of ERBB3 signaling and MAPK signaling pathways by analyzing components of the signaling pathways in addition to key components integral in these signaling pathways. We will also evaluate NRG1/HRG1 (neuregulin 1/heregulin 1, ERBB3 ligand) expression and correlate this with treatment response.

CONFIDENTIAL

This material is the property of the NYU School of Medicine and Langone Medical Center. Do not disclose or use except as authorized in writing by the study sponsor

Analysis will be performed using immunohistochemistry, Western Blot analysis (if there is enough tissue), and in situ hybridization.

